6. Poorly controlled diabetes or significant changes to diabetes medications within 6 weeks prior to Day -5.
7. Chronic obstructive pulmonary disease requiring the use of supplemental oxygen.
8. Body mass index < 18.5 or ≥ 40 kg/m².
9. History of active or chronic passage of 3 or more loose stools per day within 4 weeks prior to screening.
10. Active inflammatory or irritable bowel disorder of any grade.
11. Active or prior history of GI bleeding within 8 weeks prior to screening, as confirmed by hospitalization-related event(s) or medical history of hematemesis or hematochezia.
12. Prior transjugular intrahepatic portosystemic shunt placement.
13. Prolonged QTc on screening ECG (defined as QTc > 500 ms).
14. Renal insufficiency (defined as serum creatinine >1.5 mg/dL).
15. Apart from chronic liver disease, any acute or chronic medical, surgical, psychiatric, or social condition including history of cerebrovascular disease (stroke, transient ischemic attack) or dementia, or laboratory abnormality that may increase the patient risk associated with study participation, compromise adherence to study procedures and requirements, confound interpretation of the safety, kinetics, or pharmacodynamics results, and, in the judgment of the investigator, make the patient inappropriate for enrollment.
16. Current or anticipated treatment with systemic (e.g., oral or intravenous) antibiotic (including rifaximin) within 4 weeks prior to Day -5 through the final outpatient follow-up for any reason (e.g., infection or planned surgery, hospitalization, dental, or interventional studies) (Exception: topical antibiotics are allowed).
17. Current use of valproate, corticosteroids, or cytotoxic drugs.
18. Current or anticipated treatment for viral hepatitis within 3 months prior to Day -5 through the final outpatient follow-up.
19. Current or prior use of lactulose within 2 weeks prior to Day -5.
20. Current or prior use of probiotic supplements (excluding enriched foods such as yogurt) within 4 weeks prior to Day -5.

21. Any condition, prescription medication, or over-the-counter product that may possibly affect absorption of medications or nutrients (e.g., celiac disease, gastrectomy, bypass surgery, ileostomy).
22. Alcohol intake of more than two units per week within 1 month prior to screening.
23. Dependence on drugs of abuse, use of any opioids (except stable regimen of prescription drugs).

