24. Administration or ingestion of an investigational drug within 8 weeks or 5 half-lives, whichever is longer, prior to screening or current enrollment in an investigational study.
25. History of allergy to ranitidine, or intolerance to any of the excipients (glycerol, CVS Health Easy Fiber).

Table 2: Laboratory Exclusion Criteria

Laboratory measure	Exclusion criterion
White blood cell count	< 1×10 ⁹ /L
Hemoglobin	< 8.5 g/dL
Platelet count	< 35,000 /μL
aPTT	> 1.5 × ULN
PT	> 4.0 sec prolongation from ULN
INR	> 1.7
Serum creatinine	>1.5 mg/dL
Total bilirubin	> 50 μmol/L or > 3 mg/dL, unless diagnosed with Gilbert's syndrome
Serum Albumin	< 2.8 g/L
AST and/or ALT	> 3 × ULN
P-sodium	< 132 or > 148 mmol/L
P-potassium	< 3.2 or > 5.3 mmol/L
QTc	> 500 ms

Abbreviations: aPTT = activated partial thromboplastin time; ALT = alanine aminotransferase; AST = aspartate aminotransferase; INR = international normalized ratio; PT = prothrombin time; QTc = QT interval corrected for heart rate; ULN = upper limit of normal

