7.2.6. Clinical Laboratory Measurements

The following clinical safety laboratory tests will be performed at the time points specified in [Table 3](#): CBC with differential, prothrombin time (PT)/activated partial thromboplastin time (aPTT), serum chemistry including liver function tests (LFTs), and urinalysis. These tests will include the parameters necessary for calculation of the MELD score (i.e., serum bilirubin, serum creatinine, and INR; see [Appendix 5](#)). Screening for infectious diseases and drugs of abuse will also be performed prior to study dosing. At screening, if non-childbearing potential status is equivocal based on medical history, FSH will be assessed in selected females to confirm post-menopausal status.

Screening results will be assessed by the Investigator for inclusion of subjects in the study. Additionally, unscheduled clinical laboratory tests can be obtained at any time during the study at the Investigator's discretion. The diagnosis corresponding to any clinically significant abnormality, or abnormality requiring treatment/intervention, must be recorded as an AE.

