7.2.12. Cirrhosis Severity Grading

The severity of cirrhosis will be assessed using the Child-Turcotte-Pugh score, which reflects a composite score incorporating HE grade, extent of ascites, and bilirubin, albumin, and INR values (see [Appendix 4](#)) and MELD score calculated based on bilirubin, creatinine, and INR values (see [Appendix 5](#)).

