8.2. Study Discontinuation for Individual Subjects

Subjects must discontinue further IP administration and withdraw from the study for the following reasons:

- Withdrawal of consent;
- Investigator decision;
- Significant noncompliance with protocol procedures;
- >1 missed dose of investigational product
- Necessity for treatment with systemic antibiotics;
- Clinically significant allergy or hypersensitivity reaction to SYNB1020;
- Development of any of the following toxicities:
 - AE of Grade 3 or greater severity according to the NCI CTCAE or life-threatening AE if not covered by CTCAE;
 - Episode of clinically overt HE (West Haven grade 2 or higher; see [Appendix 2](#))
 - QTc interval of > 520 msec or an increase from baseline of > 60 msec confirmed in a repeat test after at least 20 minute;
 - Any of the following laboratory abnormalities:
 - Grade 3 liver enzyme abnormalities and 10-fold ULN for those with normal values at baseline OR a 5-fold increase or 10-fold ULN for those with abnormal values at baseline, whichever is lower;
 - Hemoglobin levels of < 8 g/dL confirmed in a repeat test or requiring blood transfusion;
 - Platelet count of < 20,000/mL confirmed in a repeat test;
 - eGFR < 30 mL/min/1.73m² confirmed in a repeat test;
 - PT > 6.0 sec over ULN or INR level of > 2.3 confirmed in a repeat test;
 - Bilirubin > 5 × ULN confirmed in a repeat test;

- Any other laboratory abnormality of Grade 3 or great severity not covered above and not present at baseline, confirmed in a repeat test.

Subjects may withdraw their consent at any time for any reason without prejudice to their future medical care by the physician or at the institution. If a subject withdraws consent, the date and stated reason for consent withdrawal should be documented. Subject data collected up to the date of consent withdrawal will be included in the analyses.

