9.6. Clinical Laboratory Abnormalities

It is the responsibility of the Investigator to assess the clinical significance of all abnormal laboratory values as defined by the appropriate reference range(s). All abnormal values assessed to be of clinical concern and at least possibly related to SYNB1020/placebo or of uncertain causality should be repeated. Persistent abnormal values and changes of possible clinical concern

that remain within the normal range should be followed at the discretion of the Investigator. Of note, due to the underlying condition under study, ammonia values will often fall outside of the reference ranges; clinical significance and follow-up of these abnormal values will be determined by the treating Investigator on an individual subject basis.

An abnormal laboratory value that is not already associated with an AE is to be recorded as an AE if an action on IP dosing is made as a result of the abnormality, if intervention for management of the abnormality is required, or at the discretion of the Investigator.

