APPENDIX 4. CHILD-TURCOTTE-PUGH SCORE TESTING

Parameter	Assign 1 Point	Assign 2 Points	Assign 3 Points
Encephalopathy grade	None	Grade 1-2 (or precipitant-induced)	Grade 3 or 4 (or chronic)
Ascites	None	Mild/moderate (diuretic-responsive)	Severe (diuretic-refractory)
Serum bilirubin (mg/dL)	< 2	2 to 3	> 3
Serum albumin (g/dL)	> 3.5	2.8 to 3.5	< 2.8
PT (sec prolonged) or INR	< 4 < 1.7	4 to 6 1.7 to 2.3	> 6 > 2.3

Abbreviations: INR = international normalized ratio; PT = prothrombin time

Source: <https://www.hepatitis.va.gov/pdf/Child-Pugh-score.pdf>

Child-Turcotte-Pugh scoring is obtained by adding the score for each parameter:

Child-Turcotte-Pugh class:

- A = 5 to 6 points
- B = 7 to 9 points
- C = 10 to 15 points

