4.6.9. Cirrhosis Severity Grading

Severity of cirrhosis will be assessed by the Child-Turcotte-Pugh score, which reflects a composite score incorporating HE grade, extent of ascites, and bilirubin, albumin, and INR values and MELD score calculated based on bilirubin, creatinine, and INR values. This will be collected during screening, Day -2 (Baseline) and Day 6.

Cirrhosis severity results will be summarized descriptively for each class at every time point it was collected. The composite Child-Turcotte-Pugh and MELD scores will also be summarized by their actual score and change from Baseline to each on study evaluation.

All cirrhosis severity data for each subject will be provided in data listings.

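### The albumin exclusion limit in Protocol Table 2 is written in g/L and is 10-fold too low to act; the platelet withdrawal limit in Section 8.2 probably has a similar unit error, subject to a check of the PDF

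*Protocol*

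**What the plan says.** **Albumin.** The eligibility criteria for Part 1 (Section 5.2.1.1, item 9) and Part 2 (Section 5.2.1.3, item 8) both refer to "Table 2: Laboratory Exclusion Criteria". Its albumin row excludes values below 2.8 g/L. Both criteria let the investigator accept an out-of-limit value that he or she considers clinically unimportant. In Appendix 4 the Child-Turcotte-Pugh row labelled "Serum albumin (g/dL" gives 1 point above 3.5, 2 points from 2.8 to 3.5 and 3 points below 2.8.

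**Platelets.** Table 2 excludes counts below 35,000 per microlitre at entry. Section 8.2 lists, among the reasons for mandatory withdrawal, a count below "20,000/mL confirmed in a repeat test".

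The current protocol text corrects neither unit, and the SAP restates neither limit.

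**The concern.** The number 2.8 appears in two places in the protocol for the same analyte, in units that differ by a factor of 10. Only one can be meant. If Table 2 is applied as printed, a patient with an albumin of 2.0 g/dL falls in the worst Child-Turcotte-Pugh albumin category but is not flagged by the table.

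For platelets, a withdrawal limit per millilitre set beside an entry limit per microlitre would leave the withdrawal limit practically unreachable.

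Safety and tolerability are the primary objective, and these limits govern who enters and who must stop dosing. A site that follows the text literally gets no numeric trigger. A site that silently reads the intended unit departs from the written protocol.

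**Working it through.** The plan gives no derived figure to reproduce. The check is unit conversion, plus a comparison with the same analyte's limit elsewhere in the protocol.

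**Albumin**
- Inputs: 2.8 g/L (Table 2); 2.8 g/dL (Appendix 4). 1 L = 10 dL.
- Written limit: 2.8 / 10 = 0.28 g/dL.
- Appendix 4 cut point: 2.8 × 10 = 28 g/L.
- Ratio: 28 / 2.8 = 10.

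The neighbouring rows show which unit was meant. Table 2 sets INR at 1.7, PT prolongation at 4 seconds and bilirubin at 3 mg/dL. Each is an Appendix 4 cut point in the matching unit. Albumin at 2.8 fits that pattern only in g/dL.

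**What else would catch low albumin**
- Child-Turcotte-Pugh: albumin below 2.8 g/dL scores 3. With the other four items at their minimum, the total is 3 + 1 + 1 + 1 + 1 = 7. Exclusion needs a total above 9, so at least 10 − 7 = 3 further points must come from encephalopathy, ascites, bilirubin or PT/INR.
- MELD: Section 7.2.12 describes a "MELD score calculated based on bilirubin, creatinine, and INR values". Albumin does not enter it, so the MELD criteria give no protection here.
- Judgement: Section 7.2.6 says "Screening results will be assessed by the Investigator for inclusion of subjects in the study", and exclusion 15 in both parts covers a "laboratory abnormality that may increase the patient risk associated with study participation", as the investigator judges it.

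**Platelets, if the printed unit is mL**
- Inputs: 20,000 per mL (Section 8.2); 35,000 per microlitre (Table 2). 1 mL = 1,000 microlitres.
- Written limit: 20,000 / 1,000 = 20 per microlitre.
- Apparent intent: 20,000 per microlitre. Ratio: 20,000 / 20 = 1,000.
- Entry limit over withdrawal limit: 35,000 / 20 = 1,750 as written; 35,000 / 20,000 = 1.75 if microlitres were meant.
- Fall needed by a subject who enters at 35,000: (35,000 − 20) / 35,000 = 99.94% as written; (35,000 − 20,000) / 35,000 = 42.9% if microlitres were meant.

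**What else would catch a platelet fall**
- Section 7.2.6 makes AE recording compulsory for the diagnosis behind a laboratory abnormality that is clinically significant or needs treatment. Section 8.2 requires withdrawal for an AE of Grade 3 or greater. Section 9.2.1 itself uses thrombocytopenia as an example of a Grade 4 event. Together these form a written route to withdrawal, but it opens only once the abnormality is judged clinically significant or is treated.
- The closing laboratory item in Section 8.2 covers Grade 3 abnormalities that the list does not already name. Platelets are named, so it arguably does not apply.
- Investigator decision remains available at any time.

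**The case against.** Three points on the other side have force.

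**The platelet unit turns on one character.** Text taken from a PDF can show µ as m. The micro sign does survive in Table 2, which makes a misreading less likely. But the Section 8.2 list contains no other micro sign to show that it survived there, and the extracted SAP text does confuse similar characters: the product code mostly appears with a letter I where a digit 1 belongs. This stands, so the platelet item is conditional. The albumin error cannot arise this way.

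**Albumin is looked at anyway.** The Child-Turcotte-Pugh score uses g/dL, and SAP 4.6.9 says of the cirrhosis scores: "This will be collected during screening, Day -2 (Baseline) and Day 6". The site therefore sees and scores the value in the correct unit before entry. Section 9.6 also makes the investigator "assess the clinical significance of all abnormal laboratory values as defined by the appropriate reference range(s". This too stands, and it limits the harm. It does not restore a limit, because a score of 7 passes and the rest is judgement.

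**Most readers would spot the typing errors.** Probably so, but an eligibility limit should not depend on readers mentally correcting it.

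A reader might infer that a subject with a dangerously low platelet count would have to stay on treatment, or that patients with low albumin would enter unseen. The documents do not support either reading. The AE route in Sections 7.2.6 and 8.2 leads to mandatory withdrawal for a severe, clinically significant platelet fall, and albumin is reviewed at screening. Because Table 2 limits can be waived, even a correct albumin limit would not be an absolute bar.

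**Conclusion.** The albumin point holds firmly. The Table 2 limit is 0.28 g/dL as written against an evident intent of 2.8 g/dL, a 10-fold error that applies to both parts. That no plausible subject would fall below 0.28 g/dL is an assumption: the documents give no albumin distribution, although Appendix 4 places the worst category at anything under 2.8 g/dL. The loss is an explicit numeric flag, with investigator judgement and a partial score criterion left in its place.

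The platelet point holds only if the original PDF prints mL. In that case the written limit is 20 per microlitre, 1,000-fold below the apparent intent, and mandatory withdrawal for a severe fall rests on a judgement of clinical significance followed by AE grading, not on the number. The intended 20,000 per microlitre is inferred from the entry limit and needs medical confirmation.

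Severity is low. Endpoints, sample size, power and type I error are unaffected.

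**What to change.** - In Table 2, change the albumin limit to < 2.8 g/dL (28 g/L), once the sponsor's medical staff confirm it.
- Check the platelet unit in Section 8.2 against the original PDF. If it reads mL, change the limit to < 20,000/µL, again with medical confirmation. If it already reads µL, no change is needed.
- Align any data-entry checks that use either limit; the documents do not say whether such checks exist.

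The cost is one unit correction, or two at most, in a clarification letter or the next amendment. Design, sample size and analysis do not change.

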9. ADVERSE EVENTS

9.1. Adverse Event

An AE is any untoward medical occurrence, including the exacerbation of a pre-existing condition, in a subject administered a pharmaceutical product regardless of causality.

9.1.1. Assessment of Severity

The severity rating of an AE refers to its intensity. The severity of each AE will be categorized using the NCI CTCAE, version 4.03.²¹ For any term that is not specifically listed in the CTCAE scale, intensity should be assigned a grade of 1 through 5 using the following CTCAE guidelines:

- Grade 1: Mild; asymptomatic or mild symptoms; clinical or diagnostic observations only; intervention not indicated
- Grade 2: Moderate; minimal, local or noninvasive intervention indicated; limiting age-appropriate instrumental activities of daily living
- Grade 3: Severe or medically significant but not immediately life-threatening; hospitalization or prolongation of hospitalization indicated; disabling; limiting self-care activities of daily living
- Grade 4: Life-threatening consequences; urgent intervention indicated
- Grade 5: Death related to AE

9.1.2. Assessment of Causality

Medical judgment should be used to determine the cause of the AE, considering all relevant factors such as (but not limited to) the underlying study indication, coexisting disease, concomitant medication, relevant history, pattern of the AE, temporal relationship to SYNB1020/placebo, and de-challenge or re-challenge.

Yes (possibly, probably, or definitely related): there is a reasonable possibility that SYNB1020/placebo caused the event; one or more of the following criteria apply:

- The event follows a reasonable temporal sequence from administration of SYNB1020/placebo.
- The event could not be reasonably attributed to the known characteristics of the subject's clinical state, environmental or toxic factors, or other modes of therapy administered to the subject.
- The event follows a known pattern of response to SYNB1020.
- The event disappears or decreases on cessation or reduction in dose. (It should be noted that in some situations an AE will not disappear or decrease in intensity upon discontinuation of study dosing despite other clear indications of relatedness).

No (unlikely, probably not related, or definitely not related): there is no reasonable possibility that the IP caused the event; one or more of the following criteria apply:

- The event does not follow a reasonable temporal sequence from administration of SYNB1020/placebo
- The event could be reasonably attributed to the known characteristics of the subject's clinical state, concurrent illness, environmental or toxic factors, or other modes of therapy administered to the subject.
- The event does not follow a known pattern of response to SYNB1020.
- The event does not disappear or decrease on cessation or reduction in dose(ing), and it does not reappear or worsen when dosing is resumed.

9.2. Serious Adverse Event

An SAE is any untoward medical occurrence that meets any of the following criteria:

- Results in death.
- Is immediately life-threatening (refers to an event in which the subject is at risk of death at the time of the event; it does not refer to an event, which hypothetically might have caused death if it were more severe).
- Requires inpatient hospitalization or prolongation of existing hospitalization.
- Results in a persistent or significant incapacity or substantial disruption of the ability to conduct normal life functions.
- Is a congenital anomaly/birth defect.
- Based on appropriate medical judgment, represents an important medical event that may jeopardize the subject or may require intervention to prevent one of the other outcomes described above.

9.2.1. Clarification of Serious Adverse Event Definition

- Death is an outcome of an SAE and not an SAE in itself. When death is an outcome, the event(s) resulting in death should be reported (e.g., “pulmonary embolism” with a fatal outcome). The appropriate diagnosis or term should be recorded and assigned severity Grade 5.
- In instances of death due ultimately to the underlying disease, the cause of death should be indicated as the specific event or condition resulting in death to the extent possible. If no appropriate term with a Grade 5 severity in the CTCAE can be identified, then a term should be selected from the CTCAE category “Death”.
- “Life-threatening” means that the subject was at immediate risk of death from the event as it occurred. This does not include an event that might have led to death if it had occurred with greater severity. Grade 4 events (e.g., thrombocytopenia) are not always serious unless they have life-threatening consequences or result in hospitalization.

- Pre-planned or elective hospitalizations including social and/or convenience situations (e.g., respite care) are excluded from SAE reporting. In addition, “admissions” under 23-hour Observation or Emergency Room visits are excluded from SAE reporting; however, such events should still be reported on the appropriate eCRF page.
- Overdose of either SYNB1020 or concomitant medication without any overdose signs or symptoms unless the event meets SAE criteria (e.g., hospitalization) are excluded from SAE reporting; however, such events should still be reported on the appropriate eCRF page.
- SAEs that occur within the safety follow-up period but are related to subsequent therapies are excluded from SAE reporting:
 - Subjects who have completed study dosing or who terminate from study and then undergo subsequent therapies during the safety follow-up period and experience an SAE specifically related to the administration of the subsequent therapy will not have those events reported as SAEs. This exclusion will include “elective” hospitalizations necessary for the administration of such therapies.

9.2.2. Serious, Unexpected, Suspected Adverse Reactions

In accordance with regulatory requirements, the Sponsor or designee will immediately notify regulatory authorities and the Investigators, who will in turn notify their IRB as necessary, of any AE associated with IP administration or study procedures that is a serious, unexpected, suspected adverse reaction (SUSAR) or any finding from tests in laboratory animals that suggests a significant risk for human subjects, including reports of mutagenicity, teratogenicity, or carcinogenicity. An AE or suspected adverse reaction is considered “unexpected” if it is not listed in the Investigator’s Brochure or is not listed at the specificity or severity that has been previously observed.

9.3. Procedures for Treating and Reporting Special Safety Events

9.3.1. Infection (Suspected or Confirmed)

Subjects who demonstrate any symptoms, signs, and/or laboratory assessments suggestive of possible infection during the dosing or follow-up periods should be assessed for infection, including blood and urine evaluation (culture and/or PCR, see [Section 7.2.9](#)). Samples of all available body fluids should be obtained for PCR assessment prior to initiating broad spectrum antibiotic treatment guided by the subject’s clinical condition and local standard of care; however, administration of antibiotics should not be significantly delayed to allow for collection (e.g., of feces). Subjects who require systemic antibiotic treatment should discontinue IP dosing and the event should be reported to the Sponsor within 24 hours. SYNB1020 is a Gram-negative bacteria with no antibiotic resistance genetic markers. Antibiotic sensitivity testing has been performed as described in the Investigator’s Brochure and can be used to guide treatment if infection is suspected.

